**Organ System \***

General Disorders

**Collection Approach \*** § (or Collection Approach for Table Default required)

Systematic Assessment: Patients will be invited for a checkup immediately after the intervention and three months after the intervention.

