# ClinicalTrials.gov Results Data Element Definitions for Interventional and Observational Studies

## ▼1. Participant Flow

Enrollment

Arms	Assigned Interventions

Experimental: Neuromuscular Electrical Stimulation (NMES) with TDT
	
Device: Procedure: Neuromuscular Electrical Stimulation with TDT
 
The skin to be treated will be cleaned and dried. NMES will be implemented with signals received from two channels. In the first channel, the upper electrodes will be placed horizontally just above the hyoid bone. This is the place where the cupping is felt when the finger is pressed right under the chin. In the second channel, the lower electrodes will be placed horizontally, just above the thyrohyoid muscle. This is the place where you can feel a cupping when pressed with your finger, on both sides of the apple in the larynx. The device will be set to start at the lowest power, with very short pulses of approximately 700 microseconds, at intervals of 1 second. The power will be gradually increased according to the device and the power that the patient feels vibration will be stopped. The power to be applied will not exceed 25 milliamps. NMES application and Traditional Dysphagia Therapy will be applied for 45 minutes a day, 5 days a week for 3 weeks.

Active Comparator: Traditional Dysphagia Therapy (TDT)
	
Behavioral: Procedure: Traditional Dysphagia Therapy (TDT)
 
Traditional dysphagia therapy includes diet modification training, teaching postural compensatory methods, training of oral motor control exercises and tongue root exercises, training of swallowing maneuvers, and practice of chin-resistance exercise, which is the exercise of opening the upper esophageal sphincter.
 
Traditional Dysphagia Therapy will be applied for 45 minutes a day, 5 days a week for 3 weeks.

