### ▼3. Outcome Measures

#### Primary Outcome Measure:

- Change in Functional Oral Intake Scale (FOIS)

Functional Oral Intake Scale (FOIS) is a scale that shows the functional oral intake of patients with dysphagia. FOIS used for evaluation is a two part scale consisting of 7 levels. It is used to show whether the individual is dependent on the feeding tube and the level of oral intake. On this scale, 7 shows the best and 1 shows the worst functional oral intake. The change in FOIS will be our primary outcome measure in our research. It has been evaluated as an appropriate tool to demonstrate the change in functional oral intake in stroke patients. It is suitable as an independent measure of functional oral intake in prospective studies of stroke-related dysphagia.

[Time Frame: before intervention, immediately after intervention, 3 months after the intervention]

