FEES will be performed by the otolaryngologist doctor before and immediately after the treatment. In the fiberoptic endoscopic swallowing assessment, the condition of the patient according to the penetration aspiration scale will be checked. Grade 1 represents the best and grade 7 the worst on the penetration aspiration scale.

[Time Frame: before intervention, immediately after intervention]

- Change in Voice-Related Quality of Life (V-RQOL) Score

This ten-item scale is a scale designed for adult populations with voice disorders to measure both social-emotional and physical-functional aspects of voice problems. The answer points for each question range from 1 (few problems) to 5 (serious problems). A total score change on this scale will be used to evaluate patients.

[Time Frame: before intervention, immediately after intervention, 3 months after the intervention]

Arms	Assigned Interventions

Experimental: Neuromuscular Electrical Stimulation (NMES) with TDT
	
Device: Procedure: Neuromuscular Electrical Stimulation with TDT
 
The skin to be treated will be cleaned and dried. NMES will be implemented with signals received from two channels. In the first channel, the upper electrodes will be placed horizontally just above the hyoid bone. This is the place where the cupping is felt when the finger is pressed right under the chin. In the second channel, the lower electrodes will be placed horizontally, just above the thyrohyoid muscle. This is the place where you can feel a cupping when pressed with your finger, on both sides of the apple in the larynx. The device will be set to start at the lowest power, with very short pulses of approximately 700 microseconds, at intervals of 1 second. The power will be gradually increased according to the device and the power that the patient feels vibration will be stopped. The power to be applied will not exceed 25 milliamps. NMES application and Traditional Dysphagia Therapy will be applied for 45 minutes a day, 5 days a week for 3 weeks.

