## ▼4. Adverse Event Information

Information for completing three tables summarizing adverse events.

1. All-Cause Mortality: \* § Mortality is not expected in our study.
2. Serious Adverse Events: \* Serious adverse events are not expected in our study.
3. Other (Not Including Serious) Adverse Events: \* Adverse event due to the study is not expected. If any adverse event will be seen it will be reported.

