### Time Frame \* §

Adverse event data will be collected between 15 April 2020 and 15 April 2021.

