### Adverse Event Reporting Description [\*]

Patients will be invited for a checkup immediately after the intervention and three months

after the intervention. When patients encounter any problem beyond the specified times, they will reach out to the researcher through the contact number given to them and report the problem.

**Collection Approach for Table Default** \* § (or *Collection Approach for each Adverse Event Term required*)

Systematic Assessment: Patients will be invited for a checkup immediately after the intervention and three months after the intervention.

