### **Arm/Group Description** \* §

Traditional dysphagia therapy and neuromuscular electrical stimulation (NMES) will be applied to 19 patients selected for the Experimental Group. NMES application and Traditional Dysphagia Therapy will be applied for 45 minutes a day, 5 days a week for 3 weeks.

Traditional dysphagia therapy will be applied to 19 patients selected for Active Comparator Group. Traditional Dysphagia Therapy will be applied for 45 minutes a day, 5 days a week for 3 weeks.

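### Cheap improvement: no systematic adverse event check is scheduled during the 3-week, 15-session treatment course; both scheduled checks come after it

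*Combined protocol and SAP*

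**What the plan says.** All references are to the combined protocol and SAP.

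- **Systematic collection.** Section 4 gives the same rule twice, as the table default (under Adverse Event Reporting Description) and for the single listed event term (under Organ System): "Systematic Assessment: Patients will be invited for a checkup immediately after the intervention and three months after the intervention".
- **Other times.** Adverse Event Reporting Description relies on the patient: "When patients encounter any problem beyond the specified times, they will reach out to the researcher through the contact number given to them".
- **General statement.** The opening of section 4 says: "If any adverse event will be seen it will be reported". It gives no method or timing.
- **Window.** The Time Frame entry gives calendar dates: "Adverse event data will be collected between 15 April 2020 and 15 April 2021". It sets no time points per patient.
- **Treatment.** Arm/Group Description says for the experimental arm: "NMES application and Traditional Dysphagia Therapy will be applied for 45 minutes a day, 5 days a week for 3 weeks". The comparator receives traditional dysphagia therapy (TDT) alone on the same timetable.
- **Event term.** The Adverse Event Term entry covers only unexpected effects on how the study runs. That is narrower than the general statement, which covers any adverse event.

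**The concern.** The arms differ in NMES exposure only during the 3 weeks of treatment. Local or short-lived effects of stimulation would be expected mainly then, and no scheduled question about adverse events is stated for that time. The first scheduled question comes once the course is over, when an early event may have resolved and been forgotten.

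At stake is how complete the adverse event listing for each arm will be. The primary outcome, sample size and type I error are not affected. The outcome list contains no safety endpoint, and the Statistical Analyses section specifies no adverse event comparison. The listing is therefore the main safety information the trial will produce on adding NMES, and with 19 patients per arm each unrecorded patient is 1/19 = 5.3% of an arm.

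**Working it through.** **1. What the first checkup's timing means.** Taken alone, the phrase could mean after each session. The outcome time frames rule this out. The primary outcome is measured "before intervention, immediately after intervention, 3 months after the intervention", which is three time points for the whole study, and for the endoscopic swallowing assessment the plan says "FEES will be performed by the otolaryngologist doctor before and immediately after the treatment". The first checkup is therefore at the end of the course.

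**2. Sessions.** Inputs: 5 days a week and 3 weeks (Arm/Group Description); 19 patients per arm, 38 in total (Overall Number of Baseline Participants).
- Per patient: 5 × 3 = 15 sessions.
- Per arm: 19 × 15 = 285 planned patient-sessions.
- Trial: 38 × 15 = 570 planned patient-sessions.

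**3. Scheduled checks against the course.** There are two, one at the end of the course and one three months later. None is scheduled before the course ends. If the first checkup falls on the day of session 15, that one session day has a check, but the preceding 14 sessions still have none.

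**4. Whether other entries fill the gap.** The general statement covers an event that someone sees, but schedules no enquiry. The Time Frame entry gives a period and no method. The contact number needs the patient to act. All three can yield reports during treatment, but none is a scheduled, prompted check.

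**5. Length of recall.** Assumption: Monday-to-Friday sessions, on days 1–5, 8–12 and 15–19. The mean session day is (15 + 50 + 85)/15 = 10.

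| First checkup | Longest recall | Mean recall over sessions |
|---|---|---|
| Day 19 (last session day) | 19 − 1 = 18 days | 19 − 10 = 9 days |
| Day 22 (next Monday) | 22 − 1 = 21 days | 22 − 10 = 12 days |

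**6. Number of events missed.** This cannot be calculated. The documents give neither an expected event rate nor a rate of capture by observation, call or recall.

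**The case against.** The strongest reply is that the plan already provides for events during treatment. Patients attend 45-minute sessions five days a week, any event seen is to be reported, the collection window has no stated gap, and a contact number is supplied. The collection entry is also a short field on a registry form, so its silence about sessions is weak evidence of what staff will do. Much of this stands. A reader might infer that treatment-period events go unrecorded, or that a patient's call is the only route outside the checkups; the general reporting statement contradicts both. What remains is that these routes are unscheduled and unprompted, and the entry that defines systematic assessment names only the two checkups.

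A reader might also infer that events are captured differently in the two arms, because the NMES instructions involve asking about sensation: "The power will be gradually increased according to the device and the power that the patient feels vibration will be stopped". The documents do not support this. That step sets the device and is not an adverse event enquiry, and both arms have the same session timetable and the same checkups.

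Finally, the zeros entered for patients affected and at risk might be read as meaning that nobody is under safety observation. They are more likely placeholders: Period(s) and Baseline Measure Data both say that study data will be supplied on completion. They play no part in this point.

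**Conclusion.** The point holds as an inexpensive improvement to data collection. It is neither a contradiction nor a statistical error. As written, the plan schedules no systematic adverse event check within the 15-session course, and the first scheduled enquiry looks back 18 to 21 days at the longest. That range assumes Monday-to-Friday sessions and a first checkup on the last session day or the following Monday.

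Transient or local events that resolve before then may be recorded, but only if noticed, volunteered or remembered. The documents do not support a statement of how many would be lost, nor a claim of bias between the arms.

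**What to change.** Amend both Collection Approach entries in section 4 so that the same short adverse event checklist is used in both arms during treatment, as well as at the two checkups. Use it at every existing session or, as a minimum, once a week, which cuts the look-back to about one week. Record any untoward event, whether or not it affects the conduct of the study, in line with the opening of section 4, and reword the Adverse Event Term entry to match.

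Cost, at an assumed 2 minutes per checklist (range for 1 to 3 minutes):
- Weekly: 38 × 3 = 114 checklists; 114 × 2 = 228 minutes, or 3.8 hours (1.9 to 5.7).
- Every session: 570 checklists; 570 × 2 = 1,140 minutes, or 19 hours (9.5 to 28.5).

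These are totals of existing staff time over the whole trial. No extra visits are needed, and treatment, sample size and significance level do not change. The downside besides staff time is that more minor events will be listed.

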**Number of Participants Affected \***

0

**Number of Participants at Risk \***

0

## ▼5. Limitations and Caveats

### Overall Limitations and Caveats

In our study, we compare two groups of patients who received therapy. However, creating a third group of patients and not applying any therapy program to this group may be more beneficial in terms of demonstrating the effectiveness of the therapies.

## ▼6. Certain Agreements

Information indicating whether there exists an agreement between the sponsor or its agent and the principal investigators (unless the sponsor is an employer of the principal investigators)

that restricts in any manner the ability of the principal investigators (PIs), after the completion of the study, to discuss the results of the study at a scientific meeting or any other public or private forum, or to publish in a scientific or academic journal information concerning the results of the study. This does not include an agreement solely to comply with applicable provisions of law protecting the privacy of participants.

### **Are all PIs Employees of Sponsor? \***

Definition: Indicate whether the principal investigator is an employee of the sponsor. Select one.

- Yes: The principal investigator is an employee of the sponsor

If "No" the following information is required:

### **PI Disclosure Restriction Type**

Definition: There are no varying agreements.

